Participants from the GLA, community advisory board, and peer counselors will be invited to a session where themes and priorities co-identified will be used to develop an action plan for what content will be included in HEMI. This session will occur in-person or through telecommunication depending on COVID-19 requirements and recommendations at the time of the study. The study team (led by PI [name]) will then refine standard modules and develop adaptive modules in response to the action plan. In a second action planning session, the study team will present the modules to the community stakeholders for comment and modification.

Aim 2: Thirty families enrolling in the standard ECS program prenatally or shortly after birth will be recruited for a pilot trial of HEMI (15 control, 15 intervention). Participants will be infants and their mothers. We will recruit mothers of infants of

TEMPLATE: RESEARCH PROTOCOL

| NUMBER | ACTIVE DATE | PAGE |
|---------|-------------|----------|
| HRP-503 | 02-04-2020 | 12 of 44 |

both sexes. Mothers will be specifically targeted (rather than other caregivers) because this is the population at the ECS program where we are delivering the intervention. ECS enrolls approximately 800 mother-child dyads per year, well exceeding our required sample size. ECS home visitors will refer all eligible pregnant participants to our research coordinators, who will contact each woman to schedule the first study visit. Inclusion criteria are: 1) child age 2 months at enrollment, 2) English or Spanish speaking, 3) maternal age > 18 years, 4) singleton, and 5) no major congenital anomalies or medical conditions requiring specialized feeding. Families will be invited to participate in this study in addition to standard ECS services and engagement in this study will not impact their ability to participate in the standard program. 1:1 randomization to the control or treatment condition will occur at the time of the baseline visit.

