The following potential adverse events will be assessed throughout the study period: occurrence of choking episodes during infant feedings (at each study visit and interventionist-led treatment session), growth faltering (monitored at each interventionist-led treatment session for infants in the treatment condition; length and weight will be monitored for all participants [i.e., treatment and control] at baseline and post-treatment), and unexpected adverse events.

Study participants will be informed of any changes to the known risks and benefits of participating in the current study, including if it is identified that treatment participants are at greater risk for adverse events. If participants in the treatment arm experience greater adverse events, possible discontinuation of the study or modification of the intervention will be considered under the guidance of the ISM.

6.5 Where applicable, list and describe the data collection tools such as surveys, data collection forms, etc. All tools described should be uploaded in the RAP Smart Form on the Local Site Documents page unless they are standardized, validated tools.

Demographics Form. Participants in both the intervention and GLA methodologies will complete a demographics form. There is a separate demographic form for each of these methodologies because the interventionist participants will be asked additional demographic details about their participating child, while GLA participants will only report their own adult demographics.

Maternal Feedback on Intervention: Maternal Feedback on the Intervention will be obtained through a quantitative survey and a qualitative interview. The quantitative survey consists of Likert scale ratings on whether they perceived the intervention as suitable, occurring at the right time, being presented clearly, and helpful; mothers will also rate satisfaction with the intervention and their confidence in implementing the recommendations made by the study team. Qualitative interviews will be conducted with each family by a research staff member who was not the study interventionist (to prevent potential bias) to obtain feedback regarding additional information that would be helpful to add to the program, content that was not helpful and could be eliminated from the program, other changes they would like to see to the program, and aspects they would like to see stay the same about the program.

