18.5 Who will review the data?

An independent safety monitor (ISM) will be identified during the start-up phase of the study timeline and will provide guidance regarding adverse events and safety issues.

18.6 The statistical tests for analyzing the safety data to determine whether harm is occurring.

ANOVAs will examine the number of adverse events in the control versus intervention group.

18.7 Any conditions that trigger an immediate suspension of research.

Study participants will be informed of any changes to the known risks and benefits of participating in the current study, including if it is identified that treatment participants are at greater risk for adverse events. If participants in the treatment arm experience greater adverse events, possible discontinuation of the study or modification of the intervention will be considered under the guidance of the ISM. Any action resulting in temporary or permanent suspension of the study will be immediately reported to the funding agency program official.

| NUMBER | ACTIVE DATE | PAGE |
|---------|-------------|----------|
| HRP-503 | 02-04-2020 | 24 of 44 |

| | |
|--|--|
| 19.0 PARTICIPANT PRIVACY | 19.1 Describe the provisions to protect participants' privacy and to minimize the intrusiveness of the study questions or procedures. |
| | Participant responses will be linked to their study ID # rather than their names. Only study staff will have access to the file linking study ID# and names. All identifying information as defined by the HIPAA Privacy rule will be removed (e.g., birthdates) 2 years after the research ends. Study staff will also receive training on information related to confidentiality and session content management. This training includes education about treatment content (e.g., responsive feeding, infant obesity risk factors) and specific treatment recommendations, strategies for active listening, skills for asking sensitive questions, and how to manage sensitive/confidential information. |
| 20.0 COMPENSATION FOR RESEARCH RELATED INJURY | 20.1 For more than minimal risk research, describe the available compensation in the event of research-related injury. |
| | Not applicable. |
| 21.0 ECONOMIC BURDEN TO SUBJECTS | 20.2 Provide a copy of contract language relevant to compensation for research-related injury. |
| | Not Applicable |
| 21.0 ECONOMIC BURDEN TO SUBJECTS | 21.1 Describe any costs that subjects may be responsible for because of participation in the research. |

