### **2. Analyses**

For Aim 1, GLA data analysis will be conducted in real-time by the participants during the session. Facilitated by Co-I [name], participants will reach consensus on overall themes and action items, such as the content to be included in each treatment module. Demographic information of stakeholders will be summarized using descriptive statistics.

**For Aim 2**, descriptive statistics of the study population will be summarized. Treatment adherence will be assessed as the number of treatment visits completed within 1 week of the monthly time window. Missed visits will trigger an analysis of the situation and attempted communication with the mother to gather additional information about why study visits were not completed. Treatment fidelity will be assessed using coding of audiotapes for 25% of the visits. The maternal feedback on the program will be conducted at the post-treatment visit, and qualitative/open ended questions will be coded and analyzed for themes for improvement of the intervention. Peer counselor feedback on the program will be assessed through interviews after all treatment sessions have been delivered. Responses to open-ended questions will be analyzed for themes and also used to further modify the intervention.

For all Aim 2 effectiveness outcome variables, analyses will be conducted using two-sample t-tests or non-parametric Wilcoxon rank sum tests to evaluate between-group differences for continuous variables, and Fisher's exact tests of contingency tables for categorical variables. Prior to conducting analyses, distributions of outcome variables will be assessed to determine the appropriate modeling approaches. All primary analyses will be conducted using intention to treat (ITT) analysis, including all individuals who were enrolled. Given the small sample size, imbalances may arise between the randomized study groups. If groups are unbalanced at baseline, these baseline variables will be included in adjusted general linear model or logistic regression models, depending on the outcome, with adjusted differences in outcomes estimated by intervention group. P-values  $< 0.05$  will be considered significant. Every attempt will be made to collect demographic and psychosocial covariate measures. However in the event of missing covariate data, we will use multiple imputation techniques to handle missing data in the statistical models.

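### Protocol 18.6 compares adverse events between arms only by ANOVA on counts, a poor fit for 15 v 15 infants with events likely to be sparse and repeatable

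*Protocol*

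**What the plan says.** Protocol 6.3 lists what is monitored: "occurrence of choking episodes during infant feedings", growth faltering, and unexpected events. Item 18.6 of the protocol form asks for "The statistical tests for analyzing the safety data to determine whether harm is occurring". The whole answer is "ANOVAs will examine the number of adverse events in the control versus intervention group". It does not say whether the unit is events or infants affected, whether event types are pooled, what alpha applies, or whether an interval will be given.

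Protocol 18.7 then states: "If participants in the treatment arm experience greater adverse events, possible discontinuation of the study or modification of the intervention will be considered". The independent safety monitor advises on that step, and no p-value is attached to it. Sections 6.3, 18.2 and 18.4 have the monitor review safety data annually and as needed.

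The SAP does not mention adverse events. In its section 2, the distribution check and the choice among t, Wilcoxon and Fisher tests are set out for Aim 2 effectiveness outcomes. The 0.05 threshold stands in the same section, and nothing extends it to safety. The trial randomises 1:1, with 15 infants per arm (Protocol 6.2).

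**The concern.** With two groups, ANOVA is the pooled two-sample t-test. It treats the mean count as the summary and judges it against within-arm variance. For counts that are mostly zero, with an occasional infant who has several episodes, that variance is driven by the very infant who is the safety signal. Extra episodes in one infant raise the mean but raise the standard error as well. Growth faltering is also closer to a state than to a count, so the number of events is not a natural measure for it.

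At stake is what the safety monitor is shown. Section 18.6 supplies the only stated method for deciding whether one arm has more events, and 18.7 refers to exactly that comparison. A p-value that crosses 0.05 where an exact test does not, or stays above it where an exact test is below, is a poor summary for that purpose.

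**Working it through.** **Inputs.** 15 v 15 infants (Protocol 6.2); ANOVA on counts (18.6); alpha 0.05 two-sided, borrowed from the SAP because none is given for safety. The documents state no event rate, power or error rate for this test, so there is no figure of theirs to reproduce. All event counts and rates below are illustrative assumptions.

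**Formula.** F = t² on 28 df. If the control arm has no events, the pooled variance is half the HEMI-arm variance s², so t = m / √(s²/15), where m is the HEMI mean. Fisher's two-sided p for k v 0 infants affected is 2·C(15,k)/C(30,k).

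**Single tables (control arm all zero).**

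- Counts 1,1,1,1: m = 4/15 = 0.267; s² = (4 − 16/15)/14 = 0.2095; t = 0.267/0.118 = 2.26; ANOVA p = 0.032. Fisher: 2·1365/27405 = 0.100.
- Counts 1,1,1,8: m = 11/15 = 0.733; s² = (67 − 121/15)/14 = 4.21; t = 0.733/0.530 = 1.38; ANOVA p = 0.177. Fisher is still 0.100.
- Counts 1,1,1,1,8: ANOVA p = 0.140; Fisher 0.042.
- Counts 1,1,1,1,1,8: m = 13/15 = 0.867; s² = (69 − 169/15)/14 = 4.12; t = 0.867/0.524 = 1.65; ANOVA p = 0.110. Fisher: 2·5005/593775 = 0.017.

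When all events fall in one arm, the two-sided permutation p on the counts themselves equals the Fisher p. The gaps are therefore not caused by Fisher discarding repeat episodes.

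**No events at all.** Both variances are zero and F is undefined. With Poisson counts the chance of this is exp(−30μ): 55% at μ = 0.02 events per infant, 22% at 0.05, 5% at 0.1.

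**Long-run type I error of ANOVA at nominal 5% (simulated, equal arms).**

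| Mean events per infant | Poisson | Overdispersed (negative binomial, k = 0.5) |
|---|---|---|
| 0.05 | 0.5% | 0.4% |
| 0.1 | 2.2% | 1.8% |
| 0.2 | 4.4% | 3.5% |
| 0.5 | 5.0% | 4.0% |
| 1 | 4.9% | 4.1% |

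For yes/no events, enumerated exactly, the highest value on the grid examined was 5.5%, at a 30% event rate.

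**Power (simulated).** For 0.2 v 0.4 events per infant, ANOVA has about 15% (Poisson) or 9% (k = 0.5). For 0.2 v 0.6, Poisson: ANOVA 38.5%, permutation 26.3%, Fisher on infants affected 20.7%.

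**Would a Poisson interval on total events do instead?** Not safely. For 15 infants with k = 0.5, actual coverage of the exact Poisson 95% CI is about 97% at 0.2 events per infant, 88% at 0.4 and 78% at 1.0.

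**The case against.** Three stronger conclusions might be drawn from 18.6, and the case against each is good.

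- *That ANOVA will raise too many false alarms.* The type I error table shows otherwise. With equal arms the test is conservative when events are sparse and close to nominal otherwise. The discrepancies concern the p-value attached to a particular table, measured against exact tests that are themselves conservative.
- *That ANOVA is the reason the trial cannot detect harm.* Low power comes from 15 per arm. In the comparison above, the exact tests have less power than ANOVA, so power is no argument for changing the test.
- *That harm is decided by ANOVA.* The safety monitor reviews the data and advises on continuing, modifying or stopping. Section 18.7 ties no p-value to action, and 18.3 records event-level detail.

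Two smaller points also stand. For a single affected infant, ANOVA gives p = 0.33 however many episodes there are, but Fisher and permutation give 1.0 just as rigidly, so that case does not separate the methods. And 18.6 says ANOVAs in the plural, so the text does not establish that event types will be summed into one number.

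None of this makes ANOVA a suitable summary of these data. The monitor is still to be given a between-arm comparison, and no other is specified.

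**Conclusion.** The point holds in a limited form. ANOVA on event counts is ill-suited to 15 v 15 infants with sparse, repeatable events. It may be undefined, its p-value for a given table can be too small (0.032 v 0.100) or too large (0.110 v 0.017), and it can weaken as episodes accumulate (0.032 to 0.177). A reader might go on to infer inflated false alarms, or that a better test would restore the ability to detect harm. The calculations support neither. Nor do the documents say that a non-significant result will be taken as proof of safety; the plan simply does nothing to prevent that reading.

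The single-table results are exact arithmetic on chosen examples. That such tables are plausible rests on assumed sparseness and clustering, because the documents give no event rates. The primary analysis is untouched.

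**What to change.** Replace the sentence in Protocol 18.6 with a descriptive table by event type: choking; choking needing medical attention; growth faltering; other. For each type give the number of infants with at least one event in each arm, the risk difference and an exact 95% CI. An interval shows what a p-value hides: with 0 of 15 infants affected, the exact upper 95% limit is still 1 − 0.025^(1/15) = 21.8%.

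Restrict the between-arm comparison to events ascertained in the same way in both arms. Protocol 18.3 has forms completed at Sessions 1, 2, 4, 5 and post-treatment for HEMI families, whereas controls have only baseline and post-treatment visits (6.2). Raw totals would therefore not be comparable under any test.

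Report total events and episodes per infant descriptively, without a Poisson interval, because episodes may cluster within infants. Give the safety monitor a line listing. State that a non-significant difference is not evidence of no harm.

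The cost is one protocol sentence, one table and a listing. The forms in 18.3 already capture choking details and any intervention required. The downside is a little extra tabulation and no single p-value for safety.

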Participants will complete home-based baseline and post-treatment study visits when the child is 2 months and 9 months of age. Families randomized to the intervention condition will participate in six treatment sessions delivered as monthly 1-hour home or virtual visits based on the desires, interests, and needs of families, when the child is 3, 4, 5, 6, 7, and 8 months of age in addition to participation in the standard ECS visits. Given the program's target of behavior change and use of behavioral strategies, interventionist-delivered HEMI sessions will be provided by advanced clinical psychology doctoral students (supervised by a licensed clinical psychologist, PI [name]) accompanied by support staff. Two peer counselor-led sessions will be delivered as 1-hour home or virtual visits, based on the desires, interests, and needs of families and peer counselors, when the child is 5 and 8 months of age. Families in the control condition will receive the standard ECS content and complete baseline and post-treatment visits.

6.3 Describe procedures being performed to monitor subjects for safety or minimize risks.

Based on the size ($n = 30$) and complexity of the trial (e.g., unblinded trial) and the minimal risk of the study intervention to participants, this study will utilize an independent safety monitor (ISM) whose primary purpose will be to provide guidance regarding adverse events and safety issues. The ISM will be a medical expert (e.g., pediatrician, nurse) who is independent of the study and able to provide external and unbiased evaluation through consultation pertaining to safety issues. This person will be available in real-time on an as-needed basis should any concerns regarding adverse events or other safety issues arise. The ISM will be identified during the study start-up phase. The ISM will review relevant participant safety data and make recommendations regarding continuation, modification, or termination of the trial due to safety risk. Communication with the ISM will occur on an as-needed basis when safety concerns arise as well as annual meetings with the study PI to discuss overall trial safety data.

TEMPLATE: RESEARCH PROTOCOL

| NUMBER | ACTIVE DATE | PAGE |
|---------|-------------|----------|
| HRP-503 | 02-04-2020 | 13 of 44 |

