24-hr Dietary Recall Interviews: Infants' dietary intake will be assessed via three random dietary recall interviews conducted by phone within +/-2 weeks of their baseline and post-treatment study visits. Trained interviewers from the Schubert Research Clinic Bionutrition Core, blinded to study condition, will employ the USDA automated multiple-pass method (AMPM), a standardized approach which has been shown to improve accuracy of dietary intake data collected (Moshfegh et al., 2008). Mothers will be provided ahead of time with visual aids to assist with estimating portion sizes during the telephone interview; visual aids will reflect age-appropriate foods, portions, and serving containers to facilitate reporting (Anater et al., 2018). Nutrition Data Systems for Research (NDSR; Nutrition Coordinating Center, University of Minnesota, Minneapolis, MN) software and foods database will be used to assess total daily energy and macronutrient intake as well as food group servings consumed.

6.6 Describe all data that will be accessed and collected during the study and how that data will be obtained (how it will be accessed).

The primary study measures listed above will all be collected for the purposes of this research study in accordance with the procedures outlined above. All research participants are also participants in the Every Child Succeeds home visiting program, and information from the ECS records may also be accessed.

6.7 If there is a long-term follow-up plan (once all research related procedures are completed), what data will be collected during this period.

There are no current plans for long-term data follow-up. However, this may be of later interest based on study outcomes, and therefore the consent form mentions the possibility that researchers may contact participants in the future about additional research.

| | |
|---|---|
| 7.0 DATA AND SPECIMEN BANKING | 7.1 If data or specimens will be banked for future use, describe where the data or specimens will be stored, how the data or specimens will be accessed, and who will have access to the data or specimens. |
| | We will retain identifiable information for 2 years after this research ends, to permit longer-term follow up. After that point, all identifying data will be destroyed, and only deidentified study data will be retained for future analyses. |
| | 7.2 If specimens are being stored, list the data to be stored or associated with each specimen. |
| | Not Applicable |

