| 23.0 CONSENT PROCESS | 23.1 Where will the consent process take place? For Aim 1, participants will review an information sheet containing all elements of consent before the first GLA visit. They will indicate their consent to participate by logging on electronically to participate in the visit. For Aim 2, the consent process will occur at the participant's baseline visit, prior to completion of any study procedures. |
| | 23.2 Is there a waiting period available between informing the prospective subject and obtaining the consent? For Aim 1, participants will have time to read the information sheet and decide whether to participate or not before the GLA visit. For Aim 2, interested mothers will be contacted by the study staff via phone. Mothers will be provided information about the study procedures and inclusion criteria will be assessed. If inclusion criteria are met and a mother is interested in participating, a baseline study visit will be scheduled when the child is around 2 months of age. At this visit, informed consent will be obtained. |
| | 23.3 Describe: 
 The role of the individuals listed in the application as being involved in the consent process. The time that will be devoted to the consent discussion. Steps that will be taken to ensure the subjects' understanding. Steps that will be taken to minimize the possibility of coercion or undue influence. |
| | |

TEMPLATE: RESEARCH PROTOCOL

| NUMBER | ACTIVE DATE | PAGE |
|---------|-------------|----------|
| HRP-503 | 02-04-2020 | 27 of 44 |

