Consent will only be obtained by trained study staff listed in the application as being involved in the consent process. Participants will be informed of the voluntary nature of their participation and the fact that refusal to participate does not in any way result in the reduction or denial of other home visiting services. They will be informed that the purpose of the study is to evaluate the effectiveness of an intervention targeting healthy infant feeding, and they will be informed regarding study procedures. They will also be told that HEMI visits will be digitally recorded for fidelity purposes. Participants will be informed that even if they agree to participate, they may withdraw their consent at any time without affecting the other services that they receive from ECS. Informed consent will be completed prior to the start of any study procedures. They will be given a copy of the consent form. Because of the possibility that some mothers will have limited literacy skills, we will read the procedures section to all mothers. Moreover, we will verbally reiterate that participation is voluntary, they can leave at any time, and that home visiting services will not be affected by their decision. A consent checklist has been developed to ensure that all components of consent are addressed.

For Aim 2, consent will be completed electronically via REDCap. The IRB approved consent will be modified to an electronic format in REDCap that includes all the same elements found on the paper document (i.e. IRB number, approval dates, and UC logo, etc.). The elements of the consent requiring a signature will be added as a generate field. The instrument includes fields to capture full name, signature, and date and time of the signature for the consenter, and witness and conditional text that states that all signatures are associated with the Subject ID# registered in the database. When completed REDCap will generate a footer that contains the long date and time the document was submitted and “Confidential” listed in the header as an added precaution to preserve the research participants confidentiality. Subjects will elect either a printed or electronic copy of the e-consent document.

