If electronic consent cannot be completed via REDCap due to lack of accessibility to internet access, or due to comfort level with using technology, a paper copy of consent will be completed. Signed copies of the consent will be printed and kept secure with all printed files for this research study.

After completion of consent, they will then be randomized into the treatment or control condition. The consent process will take less than 30 minutes.

TEMPLATE: RESEARCH PROTOCOL

| NUMBER | ACTIVE DATE | PAGE |
|---------|-------------|----------|
| HRP-503 | 02-04-2020 | 28 of 44 |

23.4 Describe how consent of the subject will be documented in writing.

A written information sheet has been established for Aim 1. For Aim 1, documentation will be not be required since all study procedures are occurring virtually and the consent form would be the only document linking participant names to the study. For Aim 2, consent will be documented through the completed fields in the REDCap e-consent form. Documentation of consent is then stored within the REDCap online capture system and will be downloaded to our secure UC lab drive.

23.5 Describe the conditions under which you believe it would be appropriate to obtain ongoing consent from the subjects.

Ongoing consent will be obtained if significant study changes require participants to complete new study procedures or other unforeseeable study changes occur that may warrant ongoing consent.

| | | |
|--|--|---|
| 24.0 WAIVER OF DOCUMENTATION OF CONSENT | 
24.1 Justification for waiver of consent documentation. Check all that apply and provide rationale for all checked items. Please note that certain combinations of the selections below may justify a waiver of documentation. Please refer to HRP-411 – MEMBER CHECKLIST Waiver of IC Documentation to determine if your study qualifies for a waiver of documentation, and which boxes to check to justify the waiver.
 | |
| |  | N/A not requesting a waiver of documentation of consent. |

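### The two weeks before the baseline visit cannot be used for diet recalls, and as written all three baseline recalls follow randomisation in an unblinded trial

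*Protocol*

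**What the plan says.** Protocol 23.1 sets the order for Aim 2: "the consent process will occur at the participant's baseline visit, prior to completion of any study procedures". Section 23.3 repeats the rule, "Informed consent will be completed prior to the start of any study procedures", and then places allocation: "After completion of consent, they will then be randomized into the treatment or control condition". Section 6.2 puts allocation at the same contact: "1:1 randomization to the control or treatment condition will occur at the time of the baseline visit".

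Section 6.5 describes diet measurement as "three random dietary recall interviews conducted by phone within +/-2 weeks of their baseline and post-treatment study visits". The callers are "Trained interviewers from the Schubert Research Clinic Bionutrition Core, blinded to study condition". Section 6.3, explaining the choice of safety monitor, refers to the "complexity of the trial (e.g., unblinded trial) and the minimal risk of the study intervention". Section 23.3 also says that all mothers are told that "the purpose of the study is to evaluate the effectiveness of an intervention targeting healthy infant feeding".

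Treatment sessions start at 3 months of age (section 6.2). In SAP section 1, infant diet diversity is the change in food groups from baseline to post-treatment, compared by arm. It is the only diet outcome worded as a change, and the only one with a power figure (SAP section 3).

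**The concern.** A diet recall collects research data, so it is a study procedure and cannot precede consent. The only earlier contacts described are the home visitor's referral and the telephone information and screening call; no earlier consent is described. Staff who used section 6.5 literally could collect data before consent. Staff who kept to section 23 would collect every baseline recall after allocation.

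The second consequence matters statistically. A baseline is cleanest when it is taken before anyone who supplies the data can know the arm. Here the mother supplies the data by self-report, and nothing in the plan blinds her or delays disclosure. If knowing the arm changed how she reported or fed, the difference would enter the change score directly. SAP section 3 intends the diet result to inform the effect size and sample size of a larger trial, so a distortion would be carried forward.

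**Working it through.** **Order of events.**

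| Step | When | Where stated |
|---|---|---|
| Referral and phone screen | Before the visit | Protocol 10.1, 12.1, 23.2 |
| Consent | At the baseline visit, before any procedure | Protocol 23.1, 23.3 |
| Randomisation | At the same visit, after consent | Protocol 6.2, 23.3 |
| Three baseline phone recalls | Up to 2 weeks either side of the visit | Protocol 6.5 |
| Session 1 | Child aged 3 months | Protocol 6.2 |

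Removing the days before consent leaves 0 to 2 weeks after the visit, all of it after allocation. The number of recalls affected is at most 30 × 3 = 90. The post-treatment window is usable on both sides.

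**The plan's own figure.** Inputs from SAP section 3: SD 1.4 food groups, 15 per arm, difference 1.4. Two-sample t-test, df 28, two-sided 0.05 (SAP section 2 gives 0.05 without saying one- or two-sided):

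- SE = 1.4 × √(2/15) = 0.511
- 95% CI half-width = 2.048 × 0.511 = 1.047
- Power from the noncentral t = 75.3%, against the stated 75%. It reproduces.

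The SD is for 3 to 9 months; I assume that it also holds for 2 to 9.

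**How much a baseline reporting difference could matter.** The documents give no such figure, so the sizes below are assumed. They take no true effect and no reporting bias at 9 months.

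| Assumed difference (food groups) | Share of half-width | False-positive rate | CI coverage |
|---|---|---|---|
| 0.1 | 10% | 5.4% | 94.6% |
| 0.25 | 24% | 7.6% | 92.4% |
| 0.5 (upper illustration) | 48% | 15.7% | 84.3% |

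The low end is the more plausible if few food groups are fed at 2 months (assumed).

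**Does delayed disclosure help on balance?** Let b0 and b9 be the between-arm reporting differences at baseline and at 9 months. The net bias in the change score is b9 − b0 now, and b9 once b0 is removed. Take b9 = 0.25 (assumed):

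- b0 = −0.1: net bias is 0.25 + 0.1 = 0.35 now and 0.25 after; false positives fall from 10.1% to 7.6%.
- b0 = +0.1: net bias is 0.25 − 0.1 = 0.15 now and 0.25 after; false positives rise from 5.9% to 7.6%.

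Net bias shrinks only if b0 and b9 have opposite signs, if b9 is zero, or if |b0| exceeds 2|b9|.

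**Room in the calendar.** Assume a 30-day month and a baseline visit k days after the 2-month date. Session 1 is then nominally due at day 30, and SAP section 2 counts a visit as adherent within 1 week, that is to day 37. A 14-day window fits if k + 14 ≤ 37, so up to about k = 23. Without the tolerance the limit is 30 − 14 = 16.

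**The case against.** The strongest reply is that this is a wording slip with no demonstrated consequence. One phrase in section 6.5 covers both visits, and the consent rule already cuts off its early half at baseline. No section says when a mother learns her arm, and the reference to an unblinded trial is an aside in the safety text. Mothers in both arms hear the study's purpose, and no session has taken place, so only knowledge of the arm could differ. A shift of 0.25 would need, for example, one treated mother in four to report an extra food group for a 2-month-old. The remedy can also increase net bias when misreporting runs in the same direction at both ages.

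Most of this stands. It rules out a claim of demonstrated bias and any promise of a net gain. It does not remove the conflict between sections 6.5 and 23, which needs no assumption about bias. It also does not make a baseline taken after allocation equivalent to one taken before the arm is known. Hoping that two unknown reporting biases cancel is not a reason to keep the present order.

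A reader might infer that the diet comparison is biased, or that the plan intends data collection before consent. The documents support neither: they leave the time of disclosure unstated, and they state the consent rule twice.

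**Conclusion.** The inconsistency is established from the text: at baseline, the two weeks before the visit cannot be used, and the three recalls follow randomisation. Bias in the food-group change score is possible, not shown, and its direction is unknown. It is probably small: at an assumed 0.1 food groups it would be a tenth of the confidence interval's half-width. The larger figures above are illustrations that rest on assumed shifts, on the borrowed SD and on no cancellation at 9 months.

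The reach is narrow. The BMI outcomes do not use the recalls. A reader might extend the point to every diet model in Protocol 17.1, but that section adjusts for baseline characteristics as needed without naming baseline diet, so the documents do not settle it. Nor does the point require randomisation to be moved. This is an inexpensive improvement that should be made, not a flaw that invalidates the trial.

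**What to change.** 1. Reconcile Protocol 6.5 with 23.1 and 23.3: open the baseline recall window at consent (0 to 2 weeks after the visit) and close it before Session 1. Keep the two-sided window at post-treatment.
2. State in Protocol 6.2 and 23.3 that the mother is told her arm only when the three recalls are done or the window closes, whichever comes first. A missed recall then cannot hold up disclosure.

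Randomisation and the intention-to-treat set need not change. If disclosure is already delayed in practice, one sentence saying so meets the second item.

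The cost is wording in three protocol sections and one phone call per family, about 30 in all, with no added visit. There are three downsides. The recall window shortens when the baseline visit falls late in the month (beyond about day 23 under the assumptions above). The 9-month recalls stay open to reporting bias. Any partial cancellation of same-direction bias is lost.
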